Data collection:

The following figure shows the different moments for data collection:

DD, demographic data; MH, medical-surgical history; GH, gyneco-obstetric history; VAS1, usual menses pain; VS, vital signs; VAS2, pain perception before the intervention; ZS1, anxiety before the intervention; VAS3, pain perception after the intervention; ZS2, anxiety after the intervention; AR1, analgesic requirements after the intervention; VAS4, pain perception 6 hours after the intervention; ZS3, anxiety 6 hours after the intervention; AR2, used drugs or other analgesic therapies up to 6 hours after the intervention.

Sample calculation:

Considering the objectives of this study, the main endpoint is the change in pain perception evaluated with a VAS. For the sample calculation a one sided alternative hypothesis, a significance level (*p* value) α of 0.01 and a power (1- β) of 0.90 ($\beta=0.1$) was established.

The following are the null hypothesis (H_0) and alternative hypothesis (H_1):

- H_0 : no differences in the change of the acute pain perception (ΔP) in primary dysmenorrhea, from before the intervention (VAS2) until the moment after the intervention (VAS3), among the control (CG) and the experimental (MG) groups.

$$\begin{aligned} \text{VAS2}_{\text{CG}} - \text{VAS3}_{\text{CG}} &= \text{VAS2}_{\text{MG}} - \text{VAS3}_{\text{MG}} \\ \Delta P_{\text{CG}} &= \Delta P_{\text{MG}} \end{aligned}$$

- H_1 : Students listening to music (MG) will have a larger pain reduction (ΔP), from the moment before the intervention (VAS2) to the moment after (VAS3) the intervention, compared to silence group (CG).

- $VAS2_{CG}-VAS3_{CG} < VAS2_{MG}-VAS3_{MG}$
 - $\Delta P_{CG} < \Delta P_{MG}$

The prevalence of primary dysmenorrhea in the students from two programs (medicine and psychology) of the School of Medicine and Health Sciences from Universida del Rosario was described as 73%, with a mean pain intensity of 5.8 (SD 2.0) using a VAS (27). Nevertheless, no studies reporting the efficacy of music listening for pain relief in dysmenorrhea has been published, therefore there are no data regarding the change of pain intensity in the studied group. Moreover, the control group will wear headphones in silence while resting in the same conditions, this type of control (placebo) has not been described in the literature and won't allow an accurate sample calculation. Due to this, the first part of the study will be done as a pilot study for a better sample calculation.

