Nonetheless, it was decided to review data in similar context to do an initial sample calculation before the pilot. As mentioned, menses pain has been compared to labor pain, therefore, three studies evaluating this pain were review (46-48). One research compared music against massage and a VAS of 6 points was used so it was not considered (46). One study compared music against control (usual care) (47), and the other compared against Hoku point massage and a control group (usual care) (48). Both studies were done in primiparous women, and pain was measured with a 0-10 point and no additional analgesia was received until the intervention (47-48). These studies reported a mean age of 26.63 (SD 4.02) years old (47); and 21.43 (SD 2.58) years old (48). If averaged, the age of the studies is 24.03 years old, similar to the mean age of our target population 19.3 (SD 2.8) (27).

The mean pain before the intervention, measured at 4 cm of cervical dilation, was 6.43 (SD 2.57) (47), and 5.58 (SD 1.29) (48). If both means are averaged, a mean perception is 6.01, which is similar to that of the target population (27). Mean score after the music intervention during the latent phase was 4.43 (SD 1.03) with a mean difference of -1.15 that corresponds to a 20% pain reduction. For the control group the mean before the intervention was 6.13 and after was 6.48 that corresponds with a mean difference of + 0.35 (increased). Comparing both differences, the change between groups was 1.58 supporting the music group (48). The other study (47) did not report mean pain scores after the intervention, but they did report a mean difference between groups of 1.68 supporting music group. Considering these reports, a mean difference between groups of 1.5 in pain relief supporting music group was established.

The following formula was used:

$$n = ((AR+1)/1) \cdot (Z[1-\alpha]+Z[1-\beta])^2 \cdot \sigma^2 / \Delta^2$$

n= sample per group

AR (allocation rate) = 1

$Z[1-\alpha] = 2.33$

$Z[1-\beta] = 1.28$

$\sigma = 2$

$\Delta = 1.5$

According to this, n=46.34. In consequence, 47 students per group was calculated. After the pilot testing a new calculation will be done with more data obtained from the studied population and the interventions to study¹.

Data analyses

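### The sample size for the pre-post pain change uses an unsourced SD of 2 that matches only the SD of a single pain score, so the stated 0.90 power rests on an unstated pre-post correlation

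*Combined protocol and SAP*

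**What the plan says.** Under Sample calculation in section 3, "the main endpoint is the change in pain perception evaluated with a VAS". The null hypothesis is "no differences in the change of the acute pain perception" between the silence and music groups, written as equality of VAS2 minus VAS3. The alternative is one-sided, with alpha 0.01 and power 0.90.

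The effect is also on the change scale: "a mean difference between groups of 1.5 in pain relief supporting music group was established". It comes from two labor-pain studies with between-group differences of 1.58 and 1.68.

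The formula then takes sigma = 2, with no source beside it and no statement of what it is the SD of. The result is 46.34: "In consequence, 47 students per group was calculated".

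The same section cites the earlier student survey, "with a mean pain intensity of 5.8 (SD 2.0) using a VAS (27"), and says of the target population: "therefore there are no data regarding the change of pain intensity in the studied group". It presents the calculation as an initial one, to be repeated after a pilot. A footnote marked as not part of the original protocol says an interim analysis was judged more appropriate than a pilot. Data analyses names a MANCOVA as a further test at p < 0.01 and lists no covariates.

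**The concern.** When the outcome is a change score, sigma in a two-sample formula has to be the SD of that change. The SD of one rating across women is a different quantity. The two are linked by the correlation between the before and after ratings in the same woman, and the plan gives no value for it.

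The 0.90 power, and with it the 47 per group, therefore depends on an assumption that is never stated. If the correlation is low, the trial could miss a true difference of 1.5 points much more often than one time in ten. If it is high, the trial is larger than its target power requires. A reader of the plan cannot tell which applies.

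**Working it through.** **Inputs from the Sample calculation section.** Difference 1.5; sigma 2; one-sided alpha 0.01 (Z = 2.33); power 0.90 (Z = 1.28); "AR (allocation rate) = 1". The pre-post correlation rho is not given, so it is treated as an assumption and varied.

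**1. The plan's own figure.** n = 2 × (2.33 + 1.28)² × 2² / 1.5² = 2 × 13.0321 × 4 / 2.25 = 46.34, rounded up to 47. This reproduces. Power at 47 per group with SD 2 is 0.905 by the normal approximation and 0.895 by the noncentral t, which is used for power below.

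**2. SD of the change if 2 is the SD of one score.** With equal SDs before and after, SD(change) = 2 × sqrt(2(1 − rho)). This equals 2 only at rho = 0.5.

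**3. Power of the change-score comparison and of ANCOVA, 47 per group, SD 2 at both times.** The ANCOVA of VAS3 on arm and VAS2 has residual SD 2 × sqrt(1 − rho²).

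| rho | SD of change | Power, change score | Residual SD, ANCOVA | Power, ANCOVA |
|---|---|---|---|---|
| 0 | 2.83 | 0.58 | 2.00 | 0.895 |
| 0.2 | 2.53 | 0.69 | 1.96 | 0.91 |
| 0.3 | 2.37 | 0.76 | 1.91 | 0.92 |
| 0.4 | 2.19 | 0.83 | 1.83 | 0.94 |
| 0.5 | 2.00 | 0.895 | 1.73 | 0.965 |
| 0.7 | 1.55 | 0.99 | 1.43 | 0.996 |

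The change-score comparison reaches 0.90 at rho of about 0.51 (0.49 by the normal approximation). Under the plan's own formula it would need 65 per group at rho 0.3 and 93 at rho 0.

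**4. Unequal SDs.** The only before/after SD pair in the documents comes from one labor-pain study: 1.29 before and 1.03 after music. Applying that ratio to 2 gives a post SD of 2 × 1.03/1.29 = 1.6. Then SD(change)² = 4 + 2.56 − 6.4 × rho, which equals 4 at rho = 0.40. The threshold falls to about 0.4, and power at rho 0.3 rises to 0.84.

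**5. Other cited SDs.** With 1.29 and 1.03 taken as they stand, SD(change) at rho 0 is sqrt(1.29² + 1.03²) = 1.65 and power is 0.98 (normal approximation). With the other study's baseline SD of 2.57 at both times, the change-score comparison needs rho of about 0.70. In that case ANCOVA power is 0.68 at rho 0, 0.72 at 0.3 and 0.81 at 0.5.

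**The case against.** The strongest defence is that the protocol is open about its ignorance. It says there are no change data, that the silence control does not allow an accurate calculation, and that the figure is initial and will be redone with data from the study population. That is fair and limits the criticism. But the footnote removes the pilot and does not say that the interim analysis re-estimates the SD, so the correction no longer has a stated mechanism. Admitting that data are missing also does not tell the reader that a correlation near 0.5 is implied.

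The survey origin of sigma = 2 is an inference. The two labor-study baseline SDs average (2.57 + 1.29)/2 = 1.93, which also rounds to 2. Those are single-time SDs too, so the mismatch remains either way. A reader might take the survey score to be usual menstrual pain, but the Sample calculation calls it only mean pain intensity.

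A reader might also infer that the trial is underpowered. The documents do not show that. VAS2 and VAS3 put the same question to the same woman around a 30-minute session, and nothing in the plan indicates that the correlation is below 0.5.

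The MANCOVA might adjust for VAS2, which would largely answer the point. But no covariates are named, and it is described only as a further test. The documents do not give enough to compute its power.

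**Conclusion.** The point holds as an unsupported variance input. It is not an arithmetic error, since 46.34 follows exactly from the stated inputs.

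With SD 2 at both times and an unadjusted change-score comparison, the stated 0.90 power needs rho of about 0.5; with a post SD near 1.6 it needs about 0.4. Over rho from 0 to 0.7, with equal SDs of 2, power runs from 0.58 to 0.99, so the direction of any shortfall or excess is not fixed by the documents.

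The conclusion rests on three assumptions: that sigma = 2 is a single-time SD, which is inferred; that the primary test compares change scores, as both hypotheses do; and that 47 per group are analysed.

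It is tempting to say that ANCOVA with sigma = 2 guarantees the power whatever the correlation. That holds only for a non-negative correlation and a VAS3 SD of at most 2. At the cited SD of 2.57, ANCOVA power is about 0.68 to 0.81 for rho from 0 to 0.5.

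**What to change.** Name the primary analysis as ANCOVA of VAS3 on arm with VAS2 as covariate, tested one-sided at 0.01 as in the sizing. State that sigma = 2 is the assumed SD of VAS3, so that the residual SD is 2 × sqrt(1 − rho²). Say that power at 47 per group is then about 0.90 or more for any rho of 0 or above, on condition that the VAS3 SD is at most 2, and give the 0.68 to 0.81 range at SD 2.57 beside it.

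If the change score is kept, state the assumed rho of about 0.5 and give the power range by rho.

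In either case, say whether the interim analysis re-estimates the SD and whether the sample size can change as a result.

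The cost is wording in Sample calculation and Data analyses. VAS2 is already collected, so naming the covariate needs no extra participants or measurements.

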The SPSS for Mac, version 20, software was used for data analyses. For qualitative variables, frequency and percentages measurements will be used. For quantitative variables, central tendency measurements, variability and variance coefficients was used.

The primary endpoint for the study will be the effect of music in pain in dysmenorrhea. The secondary endpoints will be the impact in analgesic requirements, vital signs, and anxiety quantification. Comparative analysis will be performed to evaluate if a relationship between the level of pain and analgesic requirements, anxiety levels, and vital signs exist. Finally, multivariate analysis (MANCOVA) will be conducted to further test statistical significance for the pain relieving effect of music ($p < 0.01$).

4. Ethical considerations

This study is classified as minimum risk in accordance to the established regulations by the Resolution 008430 of 1993 from the Ministry of Health of Colombia (Scientific, technical, and administrative norms for the research in health).

All participants from the study will enroll and participate on their own desire and no person will be obligated to enroll, continue or complete the study participation. The study will not expose participants to drug interventions, surgical procedures or diagnostic procedures, physical therapy or other type of intervention that will add potential risks to physical integrity of participants. The study will be conducted in the Quinta de Mutis of the Universidad del Rosario, Bogota city. Therefore, no exposure to ambient risks will be related to this research. The sole intervention patients will receive is music through headphones. For conducting this research all recommendations from Helsinki declaration by the World Medical Associations will be considered.

5. Activity chronogram

ACTIVITY	MES															
	1	2	3	4	5	6	7	8	9	10	11	12	13	14	15	16
PROTOCOL DEVELOPMENT																
SEARCH FOR ADDITIONAL FUNDING IF REQUIRED AND IRB SUBMISSION																
DATA COLLECTION																
DATA ANALYSES																
PATIENT RECRUITMENT ACCORDING TO ELIGIBILITY CRITERIA																

¹ [not in the original protocol] – Note: before doing the first intervention it was deemed more appropriate to perform an interim analysis than a pilot study -.

INTERVENTION AND DATA COLLECTION FROM INCLUDED PATIENTS			
DATA ANALYSES			
DISCUSSION OF DATA ANALYSES			
COMPLETE RESULTS REPORT			
MANUSCRIPT PREPARATION			
SUBMISSION FOR PUBLICATION			

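### The trial is sized for a one-sided VAS2-VAS3 contrast, but the only test named for the music effect is an unspecified MANCOVA; a one-sided ANCOVA of VAS3 on group and VAS2 would test that hypothesis with more power and no extra data

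*Combined protocol and SAP*

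**What the plan says.** All the relevant text is in Section 3, under the headings for the sample calculation and the data analyses.

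- **Endpoint.** The sample calculation states that "the main endpoint is the change in pain perception evaluated with a VAS". It writes the null hypothesis as equality of VAS2-VAS3 in the two groups.
- **Direction.** "For the sample calculation a one sided alternative hypothesis" is adopted, and H1 reads "Students listening to music (MG) will have a larger pain reduction".
- **Size.** Alpha is 0.01, power 0.90, difference 1.5 and SD 2. "In consequence, 47 students per group was calculated", and a new calculation is promised after the pilot. A footnote to that promise says that "before doing the first intervention it was deemed more appropriate to perform an interim analysis than a pilot study".
- **Analysis.** The data analyses section gives descriptive statistics and describes the primary endpoint only in general terms, as the effect of music on pain. It then names two analyses. In the first, "Comparative analysis will be performed to evaluate if a relationship between the level of pain and analgesic requirements", anxiety and vital signs exists. In the second, "multivariate analysis (MANCOVA) will be conducted to further test statistical significance for the pain relieving effect of music", with p below 0.01.

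Section 2.2 lists between-group comparisons of VAS3, of the VAS2-VAS3 change and of pain at 3 to 6 hours (VAS4) as separate objectives. The change comparison is one to be explored.

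**The concern.** The hypothesis is well set out: endpoint, time points, direction and alpha are all fixed. The test that decides it is not. The first analysis named relates pain to other variables and does not compare music with silence. The MANCOVA is said to test the effect further, but no earlier test is named for it to add to. Its outcomes and covariates are also missing.

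Two things follow. First, a MANCOVA statistic over several outcomes is non-directional and spreads its sensitivity over all of them. Its power is therefore not the planned 90% for a directional contrast in one outcome. Second, the contrast used for sizing is a raw change score. With a pre-intervention measurement on the same scale, ANCOVA estimates the same randomised difference from the same two measurements with less residual variance. The plan collects what it needs for the stronger analysis but does not commit to it.

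**Working it through.** **Inputs.** From the sample calculation: difference 1.5, SD 2, z values 2.33 and 1.28, equal allocation. From the same section: the only SD of 2.0 reported is that of a single pain rating in a survey of the target population (mean 5.8). The plan does not say whether its SD of 2 describes a single score or a change, so both readings are worked. The correlation r between VAS2 and VAS3 is not given. Values of 0.3, 0.5 and 0.7 are assumed, with the extremes checked. Equal variances at VAS2 and VAS3 are also assumed.

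**1. The plan's own figure.** n = 2(2.33 + 1.28)² × 2² / 1.5² = 46.34, so 47 per group. This reproduces. The value 2.33 is the one-sided 0.01 quantile, so the calculation is one-sided.

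**2. Power of the change-score t-test, SD of change 2.** The noncentrality is 1.5 / (2 × √(2/47)) = 3.636 on 92 degrees of freedom. Power is 0.895 one-sided at 0.01 and 0.840 two-sided at 0.01. The first is slightly below 0.90 because the plan uses the normal approximation.

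**3. Residual SDs.** Let s be the SD of a single score.

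- Change score: s√(2(1 − r)).
- ANCOVA: s√(1 − r²).
- Ratio of ANCOVA to change-score variance: (1 − r²) / (2(1 − r)) = (1 + r)/2, which is below 1 whenever r is below 1.

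If the SD of change is 2, the ANCOVA residual SD is therefore 2√((1 + r)/2).

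**4. One-sided power at 0.01, 47 per group, difference 1.5** (noncentral t; 92 degrees of freedom for the change score, 91 for ANCOVA).

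| Reading of SD 2 | r | Residual SD, change / ANCOVA | Power, change | Power, ANCOVA |
|---|---|---|---|---|
| SD of change | 0.3 | 2.000 / 1.612 | 0.895 | 0.983 |
| SD of change | 0.5 | 2.000 / 1.732 | 0.895 | 0.965 |
| SD of change | 0.7 | 2.000 / 1.844 | 0.895 | 0.940 |
| SD of one score | 0.3 | 2.366 / 1.908 | 0.758 | 0.923 |
| SD of one score | 0.5 | 2.000 / 1.732 | 0.895 | 0.965 |
| SD of one score | 0.7 | 1.549 / 1.428 | 0.989 | 0.996 |

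**5. Extremes.** If 2 is the SD of change, ANCOVA power falls to 0.911 at r = 0.9 and 0.903 at r = 0.95, still above 0.895. In the limit r = 1 the gain vanishes and the lost degree of freedom takes power from 0.8954 to 0.8953. If 2 is the SD of one score, at r = 0 ANCOVA has 0.895 and the change score 0.582.

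**6. Is VAS2 a usable covariate?** VAS2 is taken after allocation but before the audio is played, and the envelope does not disclose the group (Section 3, procedure). It can be used as a baseline.

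**7. The MANCOVA, as an illustration only.** Suppose that only pain responds, outcomes are uncorrelated, the pain SD is 2 and no covariate is used. An overall group test at p below 0.01 then has power 0.840 with one outcome, 0.747 with two, 0.673 with three and 0.612 with four.

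**The case against.** **The MANCOVA is a between-group test.** With group as its factor it compares music with silence, and a per-outcome group effect from it could serve if pain change were listed and read one-sided. This stands. A reader might infer that the plan has no between-group test at all, and the text does not support that. The fault is that the test is unspecified and not tied to VAS2-VAS3.

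**Sidedness is already written down.** H1 is directional at 0.01, and the analysis section repeats 0.01. One-sided 0.01 is the natural reading, and nothing contradicts it. This stands too: what is missing is a statement in the analysis section. Sidedness would also matter less under ANCOVA. Two-sided at 0.01, ANCOVA power is 0.968, 0.939 and 0.902 (SD of change 2) or 0.878, 0.939 and 0.992 (SD of one score 2), at least 0.90 in five of the six cases.

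**A change-score comparison is valid, and nothing excludes VAS2 from the MANCOVA.** Both are true. The point is therefore an improvement in efficiency and clarity and does not correct an invalid analysis. How large the gain is rests on a correlation that the plan does not have.

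**Two further inferences are tempting.** One is that ANCOVA settles the sample size at 47. It does not: the plan promises a recalculation, and ANCOVA power at 47 is slightly under 0.90 for r of 0.1 or less if 2 is the SD of one score (0.899 at 0.1). The other is that the interim analysis inflates the 1% error rate. The footnote does not say that it compares the groups, and the sentence to which it is attached concerns recalculating the sample size.

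**Timing.** Some footnotes describe the conduct of the trial in the past tense and refer to a manuscript and to a later registered protocol version. If outcome data by group have already been seen, a new primary analysis would be post hoc. That caveat stands.

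**Conclusion.** The point holds as a free improvement. The plan sizes the trial on a one-sided VAS2-VAS3 contrast and then names, for the music effect, only a MANCOVA without outcomes, covariates or sidedness. That is not the test to which the 90% power refers.

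At 47 per group and r from 0.3 to 0.7, moving from the change score to ANCOVA adds about 4.5 to 9 percentage points of power if 2 is the SD of change (0.940 − 0.895 to 0.983 − 0.895). It adds from under 1 to about 16.5 points if 2 is the SD of one score (0.996 − 0.989 to 0.923 − 0.758). These sizes depend on the assumed correlation and on equal variances. The direction does not depend on the correlation, apart from one degree of freedom that matters only as r approaches 1.

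The documents do not support saying that the plan's hypothesis is undefined, that its sidedness is contradictory, or that its error rate is inflated.

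**What to change.** In the data analyses section, add text to this effect:

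> The single primary analysis is an ANCOVA of VAS3 with allocated group as factor and VAS2 as covariate. H0 is rejected if the one-sided p-value for a lower adjusted VAS3 in the music group is below 0.01, in line with H1 of the sample calculation. The adjusted difference is reported with its two-sided 98% confidence interval. The unadjusted comparison of VAS2-VAS3 between groups is supportive. The MANCOVA, with its outcomes and covariates listed here, and the comparison of VAS4 are secondary.

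With VAS2-VAS3 as the ANCOVA outcome, the group effect has the same size, the opposite sign and the same p-value, so the declared contrast is preserved.

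In the sample calculation, state whether the SD of 2 is that of a change or of a single score. Let the planned recalculation use the ANCOVA residual SD. Add one sentence on what the interim analysis does and whether it compares the groups.

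The cost is a few sentences. VAS2 and VAS3 are already collected, and no extra students or visits are needed. The change should be dated before any outcome data are seen by group. If that point has passed, report the ANCOVA as post hoc.
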